 - Note: Appropriate source documentation (eg, tape transfer method) must be available to calculate and verify the mean wheal diameter as per study requirements. Participants who do not have historical data for any of the other SPTs as specified in the study reference manual within 6 months prior to screening will need to perform them during the screening period. All participants are required to have an SPT for birch, other trees (birch-related or unrelated), and grasses during the study screening period regardless of the availability of historical data.
- 36. Pharmacokinetic (drug concentration) and immunogenicity (ADA) samples are to be collected prior to the administration of study drug. In the event of suspected serious adverse events (SAEs), such as anaphylaxis or systemic hypersensitivity, additional samples for the analysis of ADA as well as REGN5713, REGN5714, and REGN5715 drug concentration may be collected as close to the event as practically possible.
- 37. Pharmacogenomics sub-study is optional for all participants enrolling in the main study. One DNA sample is to be collected on day 1/randomization prior to receiving the study drug, but if this sample collection was omitted at baseline, it can be collected at any subsequent visit.
- 38. Unscheduled visit procedures may be performed per PI discretion based on the reason for the visit.
- 39. Allergen-specific IgE should be drawn prior to administration of study drug at the randomization visit (visit 4).
- 40. Day 57 and/or day 85 EEU challenges may not be performed in participants who have a high symptom burden assessed due to tree pollens.
- 41. Visit 10 may not be performed in participants if they are expected to be dosed within 3 weeks after the prior EEU visit. If visit 10 is not performed, then all visit 10 assessments (without any duplication) should be performed at the last prior EEU visit (including serum pregnancy test, e-diary, dispensing rescue medications, etc)

14.3. Criteria for Potentially Clinically Significant Values (PCSV)

Protocol: R5713-5714-5715-ALG-21111 Amendment 1

Date: May 31, 2023

Parameter	PCSV	Comments
Clinical Chemis	stry	
ALT*	>3 and ≤ 5 ULN and baseline ≤ 3 ULN* >5 and ≤ 10 ULN and baseline ≤ 5 ULN >10 and ≤ 20 ULN and baseline ≤ 10 ULN >20 ULN and baseline ≤ 20 ULN	Enzymes activities must be expressed in ULN, not in IU/L. Concept paper on DILI – United States Food and Drug Administration (FDA) draft Guidance Oct 2007. Each category is calculated independently. * At least one level is required; multiple levels are optional for phase $2/3$ studies. If it is desirable to get the distribution across the different PCSV levels, additional shift table on ≤ 3 , ≥ 3 to ≤ 5 , ≥ 5 to ≤ 10 , ≥ 10 to ≤ 20 , and ≥ 20 category for baseline vs. post baseline may be provided
AST*	>3 and ≤ 5 ULN and baseline ≤ 3 ULN* >5 and ≤ 10 ULN and baseline ≤ 5 ULN >10 and ≤ 20 ULN and baseline ≤ 10 ULN >20 ULN and baseline ≤ 20 ULN	Enzymes activities must be expressed in ULN, not in IU/L. Concept paper on DILI – FDA draft Guidance Oct 2007. Each category is calculated independently. * At least one level is required, multiple levels are optional for phase 2/3 studies. If it is desirable to get the distribution across the different PCSV levels, additional shift table on ≤ 3 , ≥ 3 to ≤ 5 , ≥ 5 to ≤ 10 , ≥ 10 to ≤ 20 , and ≥ 20 category for baseline vs. post baseline may be provided
Alkaline Phosphatase	>1.5 ULN and baseline ≤ 1.5 ULN	Enzyme activity must be expressed in ULN, not in IU/L. Concept paper on DILI – FDA draft Guidance Oct 2007.
Total Bilirubin*	>1.5 and ≤ 2 ULN and baseline ≤ 1.5 ULN* >2 ULN and baseline ≤ 2.0 ULN	Must be expressed in ULN, not in μmol/L or mg/L. Categories are cumulative. Concept paper on DILI – FDA draft Guidance Oct 2007. * At least one level is required, multiple levels are optional for phase 2/3 studies. If it is desirable to get the distribution of significant level, additional shift table on ≤1.5, >1.5 to ≤2.0 and > 2.0 category for baseline vs. post baseline may be provided
(ALT or AST) and Total Bilirubin	((ALT >3 ULN or AST>3 ULN) and TBILI>2 ULN) and baseline ((ALT ≤3 ULN and AST ≤3 ULN) or TBILI ≤2 ULN))	Concept paper on DILI – FDA draft Guidance Oct 2007.
Creatinine	≥150 µmol/L (Adults) and baseline < 150 µmol/L ≥30% change from baseline and <100% change from baseline ≥100% change from baseline	Benichou C., 1994. 3 independent criteria
Blood Urea Nitrogen (BUN)	≥17 mmol/L and <17 mmol/L at baseline	Two independent criteria
Chloride	<80 mmol/L and baseline ≥ 80 mmol/L >115 mmol/L and baseline ≤115 mmol/L	Two independent criteria

Parameter	PCSV	Comments
Sodium	≤129 mmol/L and baseline > 129 mmol/L ≥160 mmol/L and baseline < 160 mmol/L	Two independent criteria
Potassium	<3 mmol/L and baseline ≥ 3 mmol/L ≥5.5 mmol/L and baseline < 5.5 mmol/L	FDA Feb 2005. Two independent criteria
Glucose Hypoglycaemia Hyperglycaemia	≤3.9 mmol/L and <lln and="" baseline="">3.9 mmol/L or ≥ LLN ≥11.1 mmol/L (unfasted); ≥7 mmol/L (fasted) and baseline < 11.1 mmol/L (unfasted); <7 mmol/L (fasted)</lln>	ADA Jan 2008.
Albumin	≤25 g/L and >25 g/L at baseline	
Hematology		
WBC	<3.0 Giga/L and ≥3.0 Giga/L at baseline (Non-Black); <2.0 Giga/L and ≥2.0 Giga/L at baseline (Black) ≥16.0 Giga/L and < 16 Giga/L at baseline	Increase in WBC: not relevant. *The default criteria. Summary by race (black and Non-black) are optional. To be interpreted only if no differential count available.
Lymphocytes (ALC)	>4.0 Giga/L and ≤4.0 Giga/L at baseline	
Neutrophils	<1.5 Giga/L and ≥1.5 Giga/L at baseline (Non-Black); <1.0 Giga/L and ≥1.0 Giga/L at baseline (Black)	International Consensus meeting on drug-induced blood cytopenias, 1991. *The default criteria. By race (black and Non-black) are optional.
Monocytes	>0.7 Giga/L and ≤ 0.7 Giga/L at baseline	
Basophils	>0.1 Giga/L and ≤ 0.1 Giga/L at baseline	
Eosinophils	(>0.5 Giga/L and >ULN) and (\leq 0.5 Giga/L or \leq ULN at baseline)	Harrison- Principles of Internal Medicine 17th Ed., 2008.
	≤115 g/L and > 115 g/L at baseline for male; ≤95 g/L and> 95 g/L at baseline for Female. ≥185 g/L and <185 g/L at baseline for Male; ≥165 g/L and < 165 g/L at baseline for Female Decrease from Baseline ≥20 g/L	Three criteria are independent. *The default criteria. By gender (male and female) are optional. Criteria based upon decrease from baseline are more relevant than based on absolute value. Other categories for decrease from baseline can be used (≥30 g/L, ≥40 g/L, ≥50 g/L).
Hematocrit	\leq 0.37 v/v and $>$ 0.37 v/v at baseline for Male; \leq 0.32 v/v and $>$ 0.32 v/v at baseline for Female \geq 0.55 v/v and $<$ 0.55 v/v at baseline for Male; \geq 0.5 v/v and $<$ 0.5 v/v at baseline for Female	Two Criteria are independent *The default criteria. By gender (male and female) are optional.

	CT 1		~		
ntistical Analysis Plan				Date: May 31,	2023
generon Pharmaceuticais, inc	c. Protocol	: K3/13-3/14-3/13	O-ALG-	ZIIII Amenan	nent I

Parameter	PCSV	Comments
RBC	<4 Tera/L and ≥ 4 Tera/L at baseline for Male; <3 Tera/L and ≥ 3 Tera/L at baseline for Female ≥7 Tera/L and <7 Tera/L at baseline for Male; ≥6 Tera/L and <6 Tera/L at baseline for Female	Unless specifically required for particular drug development, the analysis is redundant with that of Hb.
Platelets	<100 Giga/L and ≥100 Giga/L at baseline ≥700 Giga/L and < 700 Giga/L at baseline	International Consensus meeting on drug-induced blood cytopenias, 1991. Two independent criteria
Vital signs		
HR	≤50 bpm and decrease from baseline ≥20 bpm ≥120 bpm and increase from baseline≥20 bpm	
SBP	≤95 mmHg and decrease from baseline ≥20mmHg ≥160 mmHg and increase from baseline ≥20 mmHg	
DBP	≤45 mmHg and decrease from baseline ≥10 mmHg ≥110 mmHg and increase from baseline ≥10 mmHg	
Respiratory rate	< 12 per minutes and ≥12 per minute at baseline >20 per minute and ≤20 per minute at baseline	
Temperature	>= 100.4 °F/38.0 °C	

14.4. **Search Criteria for TEAE of Special Interest**

AESI	Search Criteria
Systemic or severe hypersensitivity reactions	Narrow SMQ for hypersensitivity Note: Anaphylaxis will be prospectively analyzed using the criteria discussed in the statement paper from the Second Symposium on the definition and Management of Anaphylaxis (Sampson, 2006). This would include manual adjudication of relevant PTs performed by the study medical monitor, before database lock

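### SAP 14.3 caps the starred ALT, AST and bilirubin levels and leaves the higher levels optional, so a compliant report need not count the larger rises and cannot give the number above 3 × ULN

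*SAP*

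**What the plan says.** The SAP 14.3 table gives four ALT levels and the same four for AST. The first, and the only one to carry an asterisk, is ">3 and ≤ 5 ULN and baseline ≤ 3 ULN". Above it come >5 to 10, >10 to 20 and an open-ended top level, ">20 ULN and baseline ≤ 20 ULN". The note reads "At least one level is required; multiple levels are optional" for phase 2/3 studies, and the AST and bilirubin rows say the same. It does not name the required level, and the asterisk also appears on the parameter names. The ALT and AST comments add "Each category is calculated independently". A shift table across the categories is optional.

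For total bilirubin the starred level is ">1.5 and ≤ 2 ULN and baseline ≤ 1.5 ULN" and the next is ">2 ULN and baseline ≤ 2.0 ULN". The comment says "Categories are cumulative".

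A separate combined row pairs ALT or AST above 3 × ULN with bilirubin above 2 × ULN, with no upper limit. SAP 10.2 counts a participant who has at least one post-baseline measurement meeting the criteria, and includes unscheduled values. It reports the counts by treatment group.

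**The concern.** A threshold count in a safety table should not fall as the abnormality gets worse. A closed band does this: a participant at 4 × ULN enters the starred ALT level and one at 7 × ULN does not. If the higher levels are not run, which the note allows, an arm with larger rises can show fewer abnormalities than an arm with mild ones.

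The bilirubin row adds a contradiction. A cumulative level above 1.5 × ULN must include everyone above 2 × ULN, and the written definition excludes a participant whose only raised value is there. Two programmers could follow the same row and produce different counts.

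The ALT and AST band also ends where a protocol threshold begins. Protocol 7.3.2.2 singles out isolated AST or ALT above 5 × ULN, and an isolated rise of that size has no PCSV count that the SAP clearly commits to.

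**Working it through.** The plan states no figure to reproduce, so the check applies the definitions as written.

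**Inputs.** Levels and baseline conditions come from SAP 14.3, and the any-measurement rule from SAP 10.2. The test records are assumed, each with a baseline of 1 × ULN.

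**Rule.** A participant counts at a level with lower bound L, upper bound U and baseline bound B if baseline ≤ B and any post-baseline value v satisfies L < v ≤ U. The comparator is an open level, v > L, with the same baseline condition.

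**ALT or AST**

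| Post-baseline values (× ULN) | >3–5 (starred) | >5–10 | >10–20 | >20 | Open >3 |
|---|---|---|---|---|---|
| 4 | yes | no | no | no | yes |
| 6 | no | yes | no | no | yes |
| 12 | no | no | yes | no | yes |
| 25 | no | no | no | yes | yes |
| 12, 4, 1 | yes | no | yes | no | yes |
| 12, 6, 2 | no | yes | yes | no | yes |
| 12, 7, 4 | yes | yes | yes | no | yes |

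For five participants with single peaks of 4, 4, 7, 15 and 25 × ULN, the starred band counts 2 and the open level counts 5. Put the two peaks of 4 in one arm and the peaks of 7, 15 and 25 in another. The starred counts are then 2 and 0, and the open counts are 2 and 3, so the order of the arms reverses.

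**Adding the bands.** Suppose one arm has one participant with values 12, 7 and 4. Another has three participants with single values of 12, 7 and 4. Both arms show 1, 1, 1 and 0 across the four bands. The numbers of participants above 3 × ULN are 1 and 3. Band counts alone cannot tell these arms apart.

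**Total bilirubin**

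| Post-baseline values (× ULN) | >1.5–2 (starred) | >2 | Cumulative >1.5 |
|---|---|---|---|
| 1.8 | yes | no | yes |
| 2.5 | no | yes | yes |
| 4 | no | yes | yes |
| 4, 1.7 | yes | yes | yes |

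For single peaks of 1.7, 1.8, 2.5 and 4 × ULN, the starred level counts 2 of 4 and a cumulative level counts 4 of 4.

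**Scale.** With 73 participants per arm (SAP 2.2), one omitted participant is 1/73 = 1.4% of an arm.

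**The case against.** A reader might infer that the starred band is the only required level and that larger rises are counted nowhere. The documents do not support either statement. The note asks for at least one level and names none. All four ALT and AST levels are listed as criteria, SAP 10.2 does not restrict the count to the starred one, and for a baseline up to 3 × ULN the bands together cover every value above 3 × ULN. A participant is lost only if the sponsor drops levels that it wrote into its own table, which the note permits but does not plan.

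Other outputs also carry large rises. Descriptive statistics by visit and arm include the maximum (SAP 4 and 10.2). Protocol 9.1.1 has some isolated abnormal results reported as adverse events. The combined liver row has its own open-ended definition, so the closed bands do not weaken it. Protocol 8.2.3.4 requires significantly abnormal results to be repeated, and a later value inside the band would bring the participant into it. No hepatic risk is among the important potential risks in Protocol 3.3, and ALT above 3 × ULN at screening is listed among the exclusionary laboratory findings.

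All of this stands, and it limits the consequence. It does not remove the defect. A mean or a maximum is not a count of participants. Entry through a retest depends on when the retest was taken, not on how high the peak was. The combined row needs bilirubin above 2 × ULN as well. Reporting every band still leaves the number above 3 × ULN undetermined. The bilirubin contradiction is there on any reading.

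**Conclusion.** The point holds within these limits. A report that complies with SAP 14.3 could omit from every single-analyte PCSV count a participant whose ALT or AST rises all exceed 5 × ULN. Even with all bands run, the number above 3 × ULN cannot be obtained by adding them. For bilirubin, a participant reaching only 2.5 × ULN is missing from a level described as cumulative, though counted at the >2 × ULN level if that is run.

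The omission of large ALT or AST rises assumes that the optional levels are not reported and that no other value falls inside the band. The non-additivity and the bilirubin contradiction need neither assumption. The documents give no event rates, so the test records show how the rule behaves and not how often it would matter. The primary endpoint, power and type I error are unaffected. Severity is minor to moderate: a counting rule for a by-arm safety output is wrong as written and is easily corrected.

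**What to change.** In SAP 14.3, define open-ended levels with matching baseline conditions:

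- ALT and AST: >3 × ULN (baseline ≤3), >5 (baseline ≤5), >10 (baseline ≤10), >20 (baseline ≤20).
- Total bilirubin: >1.5 × ULN (baseline ≤1.5), >2 (baseline ≤2). The comment that the categories are cumulative is then true.

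Replace the note on optional levels with a statement that all levels are reported. If bands are wanted, assign each participant to one band by the worst post-baseline value, for example in the shift table already mentioned. The combined liver row needs no change.

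The cost is an edit to three rows of an appendix table and to the matching program. No new data are needed.

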14.5. Sensitization Status by SPT or sIgE

Sensitization status will be determined by SPT and sIgE testing. For SPT, a negative control (such as saline/diluent), and positive control (histamine) will be included. The SPT and sIgE tests used to evaluate sensitization status (including definitions of birch, birch-related, and unrelated allergens) are provided in the table below.

Summary of SPT and sIgE Tests Used to Evaluate Sensitization Status

Type	Group	Allergen	Tests
Birch Allergens	Tree pollens	European White Birch	SPT, sIgE
		Bet v 1	sIgE
		Bet v 2	sIgE
Birch-Related Allergens	Tree pollens	White Alder	SPT
		Grey Alder	sIgE
		American Hazel	SPT
		Red Oak	SPT, sIgE
	Tree pollens	Sugar Maple	SPT
		White Poplar	SPT
		American Elm	SPT
		Mountain Cedar	SPT
		White Ash	SPT
	Grass pollens	Grass mix ¹	SPT
Unrelated Allergens Anir		Timothy grass	sIgE
	Weed pollens	Short Ragweed	SPT, sIgE
	Animal	Cat	SPT, sIgE
		Dog	SPT, sIgE
	House dust mite	House Dust Mite Mix ²	SPT
		Dermatophagoides farinae	sIgE
		Dermatophagoides pteronyssinus	sIgE
	Mold	Mold mix ³	SPT
		Alternaria	sIgE

^[1] Grass Mix: Kentucky Bluegrass, Meadow Fescue, Orchard Grass, Perennial Ryegrass, Redtop, Sweet Vernal Grass, Timothy Grass.

^[2] House Dust Mite Mix: D. farinae, D. pteronyssinus.

^[3] Mold Mix: Alternaria alternata, Aspergillus niger, Bipolaris sorokiniana; Cladosporium sphaerospermum, Penicillium chrysogenum var. chrysogenum

Several distinct definitions of sensitization status (by either SPT or sIgE) will be used and are defined below.

- Mono-sensitization: defined as sensitization to birch and birch-related allergens only.
- Poly-sensitization: defined as sensitization to birch and birch-related allergens *and* sensitization to any unrelated allergen and specifically the following groups will be described based on sensitizations
 - Sensitization to non-tree pollens: defined as sensitization to either grass or weed pollens.
 - Sensitization to unrelated tree pollens: defined as sensitization to any unrelated tree pollen
 - Indoor perennial allergen sensitization: defined as sensitization to any of house dust mite, cat or dog.

Note:

- Sensitization by SPT: defined as a mean wheal diameter of at least 3 mm or greater versus negative control. The eligibility criterion for birch sensitization by SPT requires a mean wheal diameter at least 5 mm greater versus negative control. SPT mean wheal diameter is defined as ([longest diameter + longest perpendicular]/2).
